## **Protocol Synopsis**

Title	A Prospective, Non-Randomized, Unblinded Study Evaluating the Treatment with the Cryo-Touch III Device for Upper Limb Spasticity					
Study Device	Cryo-Touch III (a.k.a. PCP 1.0)					
Study Objective	The Cryo-Touch III study is a post-market, off-label, prospective, multicenter study of the Cryo-Touch III Device for treatment of Upper Limb Spasticity.					
	The objective of the Study is to evaluate the temporary relief of pain and symptoms in the upper arm in subjects with Upper Limb Spasticity secondary to Stroke, Cerebral Palsy, Multiple Sclerosis, traumatic brain injury or similar disorder.					
Treatment Groups	Single					
Duration of Study	Enrollment and follow-up is expected to take approximately 4 months. A subject will participate for approximately 10 weeks.					
Study Population	Male or female subjects, ages 18 and older, diagnosed with pain due to severe spasticity of the upper limb(s).					
Total Number of Subjects	Up to 20. A minimum of 10 and a maximum of 20 subjects.					
Number of Sites	1-2					
Inclusion Criteria	Eligible subjects must meet the following criteria:					
	
 
Male or female, 18 years of age and older.
 
Trial participants must have a confirmed diagnosis that results in spasticity involving muscle innervated by the musculocutaneous nerve (MCN).
 
Any medications must be maintained on a stable schedule for at least two weeks prior to treatment. No washout period is allowed.
 
Must have an average score on the Modified Ashworth Scale for Spasticity of ≥ 2 over the last 30 days in the elbow.
 
Subject, in the Investigator's opinion, will not be exposed to unacceptable risk by participation.
 
					
Exclusion Criteria	A subject is ineligible if one or more of the following criteria applies:					
	
 
Previous surgical intervention that altered the target neural anatomy of the upper limb.
 
Any injection (neurolytic, sclerosing, anesthetic, etc.) to the upper limb within the last 4 months.
 
Current enrollment in an investigational drug or device study that specifically targets spasticity management.
 
Allergy or intolerance to local anesthesia.
 
					

## CONFIDENTIAL & PROPRIETARY Page 3 of 45

	
 
Any local skin condition at the treatment site that in the investigator's opinion would adversely affect treatment or outcomes.
 
Any chronic medication use (prescription, over-the-counter, etc.) that in the investigator's opinion would affect study participation or subject safety.
 
Diagnosis of cryoglobulinemia, paroxysmal cold hemoglobinuria, cold urticaria, Raynaud's disease, open and/or infected wounds.
 
Diagnosis of progressive neurologic diseases such as ALS.
 
For any reason, in the opinion of the investigator, the subject may not be a suitable candidate for study participation (i.e., history of noncompliance, drug dependency, any related upper limb injury, etc.).
 

Study Visit Schedule	
 
Visit 1/Screening (-30 Days to Day 0)
 
Visit 2/Treatment (Day 0)
 
Visit 3/ Maintenance (Day 7)
 
Visit 4/ Maintenance (Day 30)
 
Visit 5/Study Exit (Day 56) – Telephone Follow-Up
 

Primary Outcome	A decrease in pain and symptoms caused by hypertonia of the upper arm as measured by an improvement of 1 point or greater on the Modified Ashworth Scale at Day 7.
Secondary Outcomes	
 
Improvement in spasticity as measured by the Tardieu Scale.
 
Improvement in spasm frequency and intensity as measured by the Penn Spasm Score.
 
Improvement in upper extremity motor recovery as measured by the Fugl-Meyer Scale (post stroke subjects only).
 
Subject assessed change in Mean Spasticity Numerical Rating Scale (NRS) Score.
 
Improvement in pain as assessed by visual analog scale (VAS).
 
Duration of treatment effect.
 

## **CONFIDENTIAL & PROPRIETARY** Page 4 of 45

### 1. Introduction

### 1.1.Background

Spasticity, common in neurological disorders, is part of the upper motor neuron syndrome displaying increased tone, clonus, spasms, spastic dystonia and cocontractions. The impact of spasticity on the patient varies from a subtle neurological sign to severe spasticity causing pain and contractures. Upper limb spasticity (ULS) is the rapid contraction or shortening of the muscles in the arm causing abnormal muscle movements in the elbow, wrist and fingers. It has been reported that over 1 million Americans with traumatic injury to the brain or spinal cord, stroke, multiple sclerosis and cerebral palsy experience ULS. Tightly clenched fists, twisted wrist and elbow joints, and fixed arms in flexed positions result in extreme discomfort, pain and spasm. A nonsurgical, minimally invasive, effective approach to pain associated with ULS is desirable.

Myoscience, Inc. (Redwood City, CA) has developed a pain management device – the Cryo-Touch III – for a novel, minimally invasive procedure using focused cold therapy to target sensory nerve tissue and offer long-lasting pain relief through cryoanalgesia. The device operates on the well-established cryobiology principle that localized exposure to controlled, moderately low temperature conditions can alter tissue function. The therapy treats nerves via a probe in the form of an assembly of small diameter needles, creating a highly localized, low temperature treatment zone around the probe. This focused cold therapy creates a conduction block that prevents nerve signaling. Prior studies of the Cryo-Touch, Cryo-Touch II, Cryo-Touch III (a.k.a. PCP 1.0) devices have provided preliminary evidence of effectiveness on motor nerves and have been shown to be safe with no serious device-related adverse events.

### **1.2. Device Description**

The Cryo-Touch III Device (a.k.a. PCP 1.0) (Figure 1) is a minimally invasive needle-based device. The device consists of a re-usable portable Control Unit, Handpiece, single use Cryoprobes (Figure 2) and Cryogen Cartridges. The Control Unit and Handpiece are powered by the Control Unit utilizing connection to a standard power outlet. The system is microprocessor controlled. Its functionality is driven by an operator controlled on/off switch. The unit displays indicator lights to guide the operator.

The system produces the desired effects through initiation of a cooling cycle. Each cooling cycle is initiated by subcutaneous insertion of the Cryoprobe into the selected site and activation of the cryogen flow. A freezing zone forms around the tip of the Cryoprobe and the adjacent tissue. The Cryogen Cartridges are provided in individually sealed pouches. Each cartridge contains a nitrous oxide cylinder encased with a safety cap and filter.

# CONFIDENTIAL & PROPRIETARY

Page 8 of 45

The Cryoprobes are supplied in sterile packaging and are single-patient use. The Cyroprobe tips are closed, therefore no cryogen enters the insertion site. A skin warmer provides warming at the base of the Cryoprobe tips to keep the skin surface above freezing temperatures.

- A. Control Unit
  - B. Handpiece
  - C. Cryoprobe
- D. Cryogen Cartridge

A. Skin WarmerB. Cryoprobe Tips

Figure 1. Picture of Cryo-Touch III Device.

Figure 2. Picture of the Cryoprobe.

### 1.3. Regulatory Status

The myoscience Cryo-Touch III Device has been cleared by the US FDA as a class II medical device, K120415. Approved indications include general tissue

## CONFIDENTIAL & PROPRIETARY Page 9 of 45

destruction during surgical procedures and cryo-treatment of peripheral nerves to block pain.

### 2. Study Protocol

### 2.1.Design

This is an 8 week, post-market, prospective, non-randomized, unblinded multicenter study of the Cryo-Touch III Device for treatment of Upper Limb Spasticity.

The study device is being studied per its current labeling in a currently contraindicated population.

### 2.2.Study Duration

Study enrollment and follow-up is expected to take approximately 4 months.

### 2.3.Sample Size

Up to 20 subjects will be enrolled in the study. A minimum of 10 subjects and a maximum of 20 subjects will be included.

Male and female subjects will be included without discrimination by gender, and subjects of all races and ethnicities will be equally eligible to participate in the study.

### 2.4. Subject Inclusionary Criteria

- 1. Male or female, 18 years of age and older.
- 2. Confirmed diagnosis that results in spasticity involving muscle innervated by the musculocutaneous nerve (MCN).
- 3. Stable use of medications (if applicable) for  $\geq$  two weeks prior to treatment. No washout period is allowed.
- 4. Average score on the Modified Ashworth Scale for Spasticity of  $\geq 2$  over the last 30 days in the elbow.
- 5. Subject, in Investigator's opinion, will not be exposed to unacceptable risk by participation.

### 2.5. Subject Exclusionary Criteria

- 1. Previous surgical invention that altered the target neural anatomy of the upper limb.
- 2. Any injection (neurolytic, sclerosing, anesthetic, etc.) to the upper limb within the last 4 months.
- 3. Current enrollment in an investigational drug or a device study that specifically targets spasticity management.

# CONFIDENTIAL & PROPRIETARY

Page 10 of 45

- 4. Allergy or intolerance to local anesthesia.
- 5. Any local skin condition at the treatment site that in the investigator's opinion would adversely affect treatment or outcomes.
- 6. Any chronic medication use (prescription, over-the-counter, etc.) that in the investigator's opinion would affect study participation or subject safety.
- 7. Diagnoses of cryoglobulinemia, paroxysmal cold hemoglobinuria, cold urticaria, Raynaud's Disease, open and/or infected wounds.
- 8. Diagnoses of progressive neurologic diseases such as ALS.
- 9. For any reason, in the opinion of the investigator, the subject may not be a suitable candidate for study participation (i.e., history of noncompliance, drug dependency, any related upper limb injury, etc.).

### 2.6.Schedule of Events

See Appendix B.

#### 2.6.1. Visit 1/Screening (Day -30 to Day 0)

Potential subjects will undergo screening against the study's eligibility criteria. Subjects will be informed of all study activities and requirements. After the subject has met all criteria and had ample opportunity to ask and have questions answered, an informed consent form will be signed and a copy provided to the subject.

The investigator, or designee, will document the subject's medical history, demographic information, concomitant medications/concurrent procedures, and any other required data points.

The subject will be scheduled for the next visit. The Visit 1/ Screening and Visit 2/ Treatment may occur on the same day. Every effort will be made to reduce the time between Screening and Treatment Visits if possible.

#### 2.6.2. Visit 2/Treatment (Day 0)

#### 2.6.2.1. Pre-Treatment/Evaluation Preparation

No special preparation by the subject is required prior to the treatment. The investigator will reaffirm eligibility criteria and the subject's willingness to continue participation in the trial. Any changes in concomitant medications/concurrent procedures will be recorded. Any adverse events that may have occurred prior to treatment will be documented as a change in medical history.

### **MYOSCIENCE** CONFIDENTIAL & PROPRIETARY Page 11 of 45

The target nerves will be located using adjacent anatomic landmarks. Non-invasive ultrasound imaging of the treatment area may be captured. Nerve stimulation may be used to assess location of nerves via a percutaneous nerve stimulator or a transcutaneous nerve stimulator.

The Cryo-Touch III Device will be used per the Instructions for Use on awake subjects who are prepared with dermal anesthesia only. The skin in the treatment area will be cleansed with alcohol. Local anesthetic will be injected into target sites with the goal of complete cutaneous anesthesia at the target treatment areas prior to the treatment.

The target of treatment are the musculocutaneous nerves (peripheral nerves). The nerves will be treated in a linear fashion to block the nerve at a location deemed appropriate by the investigator (see Figure 3).

Figure 3: Nerve map of intended treatment.

## CONFIDENTIAL & PROPRIETARY Page 12 of 45

#### 2.6.2.2. Treatment

The Cryo-Touch III Device will have been prepared by the trained investigator (or Sponsor designee) according to the Instructions for Use (IFU) as provided by myoscience (see supplementary material). Representatives of myoscience may be present at the treatment. Photography and videography may be captured during the treatment.

Varying treatment algorithms will be pre-determined by the sponsor and placed into cohorts as appropriate for analysis. This is intended to determine the most effective method of treatment and to optimize the algorithm. Algorithms may include the following parameters: length of treatment, number of treatment cycles, probe tip design, and probe length.

If at any time the device does not perform as expected, the investigator (or designee) will follow procedures as outlined in the IFU.

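### Section 2.6.2.2 means the cohorts to determine the most effective algorithm, a conclusion that 10 to 20 non-randomised, unblinded subjects cannot support

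*Protocol*

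**What the plan says.** Section 2.6.2.2 (Treatment) states: "Varying treatment algorithms will be pre-determined by the sponsor and placed into cohorts as appropriate for analysis". The next sentence gives the only purpose the protocol states for the cohorts: "This is intended to determine the most effective method of treatment and to optimize the algorithm". It then lists what may differ between algorithms: "Algorithms may include the following parameters: length of treatment, number of treatment cycles, probe tip design, and probe length".

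The design around this is fixed elsewhere:

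- Section 2.1 describes a "prospective, non-randomized, unblinded multicenter study of the Cryo-Touch III Device".
- Section 2.3 sets the size: "A minimum of 10 subjects and a maximum of 20 subjects will be included".
- The synopsis objective covers spasticity "secondary to Stroke, Cerebral Palsy, Multiple Sclerosis, traumatic brain injury or similar disorder".
- Section 3.1.1 defines the primary outcome as a gain of at least 1 point on the Modified Ashworth Scale at Day 7, rated by the same investigator at every time point.
- The synopsis lists a single treatment group, and neither its objective nor any listed outcome compares algorithms.

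**The concern.** Determining which of several methods works best is a comparative conclusion. It needs groups that differ, apart from chance, only in the method, and enough subjects for the true best to stand out. The protocol provides neither.

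The sentence therefore allows the cohort with the highest observed response to be read as the most effective algorithm. Its lead could instead come from its mix of causes or baseline severity, its site, operator experience at the time, the rater's knowledge of the treatment, or luck. Its observed response rate would also be too high on average, because it was singled out for being high. An algorithm carried forward on that basis would rest on a comparison the design cannot make.

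**Working it through.** **Step 1: comparability (no arithmetic).** Allocation is not random, so cohorts may differ in any prognostic feature, whoever places subjects in them. The study is unblinded, so nothing keeps the rater from knowing which algorithm was used. Having one investigator do all ratings reduces variation between raters, which is the reason Section 3.1.1 gives, but it does not remove expectation. More subjects would not cure either problem, and neither could an analysis plan.

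**Step 2: chance alone.** The protocol gives no figure to reproduce. From the documents I take a total of 10 to 20 subjects and a binary Day 7 response. The rest is assumed: *k* equal parallel cohorts of *n*, a single pick of the highest responder rate with ties broken at random, no dropout, cohorts comparable, and true response rates shown over a range.

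*Picking the better algorithm.* One algorithm has rate p₁ and the others p₀. Let b(x) be the binomial(n, p₁) probability, and let f(x) and F(x) be the binomial(n, p₀) probability and cumulative probability. Then

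P(correct pick) = Σₓ b(x) · [F(x)^k − F(x−1)^k] / [k · f(x)].

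Worked case: four cohorts of 5, 70% against 50%.

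| x | b(x) | bracket ÷ k·f(x) | product |
|---|---|---|---|
| 0 | 0.0024 | 0.0000 | 0.0000 |
| 1 | 0.0284 | 0.0020 | 0.0001 |
| 2 | 0.1323 | 0.0490 | 0.0065 |
| 3 | 0.3087 | 0.2986 | 0.0922 |
| 4 | 0.3602 | 0.7119 | 0.2564 |
| 5 | 0.1681 | 0.9541 | 0.1604 |

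The sum is 0.515 (0.5155 before rounding), or 52%. The same formula gives:

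| True rates | 2 of 10 | 2 of 5 | 3 of 6 | 4 of 5 | 5 of 4 | 5 of 2 |
|---|---|---|---|---|---|---|
| 70% v 50% | 82% | 74% | 63% | 52% | 42% | 34% |
| 80% v 50% | 92% | 84% | 77% | 67% | 56% | 42% |
| 80% v 30% | 99% | 95% | 94% | 89% | 81% | 63% |

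*Overstatement in the best-looking cohort when all algorithms are equal.* The expected best rate is (1/n) Σ_{x=1..n} [1 − F(x−1)^k]. For four cohorts of 5 at a true 50%, F(0) to F(4) are 1/32, 6/32, 16/32, 26/32 and 31/32. The sum is 1.0000 + 0.9988 + 0.9375 + 0.5642 + 0.1193 = 3.620, and 3.620/5 = 72%.

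| True rate, all equal | 2 of 10 | 2 of 5 | 3 of 6 | 4 of 5 |
|---|---|---|---|---|
| 50% | 59% | 62% | 67% | 72% |
| 30% | 38% | 41% | 46% | 51% |

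*Apparent differences when all algorithms are equal.* For two cohorts of 10 at 50%, P(equal counts) = C(20,10)/2²⁰ = 0.176 and P(counts differ by 1) = 2·C(20,9)/2²⁰ = 0.320. A gap of 20 points or more therefore occurs with probability 1 − 0.176 − 0.320 = 0.50 (0.46 at a true 30%). For four cohorts of 5, the best and worst differ by 40 points or more with probability 0.77 (0.71 at a true 30%).

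**The case against.** The best defence is that this is one sentence of intent in a procedures section. The objective is symptom relief, there is one treatment group, no outcome compares algorithms, and the sentence goes on to speak of optimising, which suits a device still being tuned. That stands in part: no declaration of a winner is otherwise planned, so the harm depends on the sentence being acted on. But it is the only purpose stated for cohorts formed for analysis, and it speaks of determining, not exploring.

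A second defence is that the figures describe fixed, equal, parallel cohorts judged once on the Day 7 responder rate. The text would equally allow stepwise tuning, or a choice based on other measures. That also stands. The figures illustrate chance under one layout and do not predict this trial. The comparability problem does not depend on them.

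Three stronger readings are tempting, and the documents do not support them:

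- A reader might infer that so few subjects could never identify a better algorithm. The tables show otherwise: with comparable cohorts, two of 10 pick correctly 82% of the time at a 20-point gap, and four of 5 do so 89% of the time at a 50-point gap.
- A reader might infer that every combination of the four listed parameters is to be tried. The text says only that algorithms may include them and describes no crossing.
- A reader might count the unstated number of cohorts as a fault. It may be set in an analysis plan or sponsor plan not shown, and I place no weight on it.

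**Conclusion.** The point holds as a fault in the stated aim. Determining the most effective method is more than a non-randomised, unblinded study of 10 to 20 subjects with mixed causes of spasticity can support. The main reason is that nothing makes the cohorts comparable, and this needs no numerical assumption.

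Chance is a second reason, and its size depends on the layout. It is modest with only two cohorts, or with a large gap at full enrolment. It is serious with several cohorts and a moderate gap, where the better algorithm is picked about half the time or less (four of 5, 52%; five of 4, 42%). Spreading 10 subjects over five cohorts gives only 63% even at a 50-point gap. Among equal algorithms at a true 50%, the apparent winner is overstated by about 9 points (two of 10) to 22 points (four of 5). These figures rest on the assumptions in the working and leave out bias from allocation and rating.

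The primary outcome is not invalidated, and varying the settings is not itself at fault. The sentence should be changed, but it does not stop the study.

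**What to change.** Replace the sentence on purpose in Section 2.6.2.2 with:

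> Algorithms are varied to explore treatment settings and inform the choice of algorithm for later study; cohort results are descriptive, all cohorts are reported, and no algorithm will be declared most effective from this study.

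Reporting every cohort matters because it stops the highest rate from being shown alone. The change does not remove confounding or unblinded rating; it limits what may be concluded in their presence.

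The cost is one sentence in an amendment, which Section 5.3.2 requires the IRB to approve before use. No subjects, visits or data are added. The sponsor gives up a claim of the best algorithm from this study but keeps the cohort data for planning. No device setting is proposed here.

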#### 2.6.2.3. Post-Treatment

Upon completion of treatment, the treatment area will be cleansed and the skin will be left undressed. Pressure to the treatment area with gauze for 5-10 minutes may be applied to minimize bleeding. The subject will be instructed in post-treatment care.

The subject will be instructed to report any adverse events or treatment side effects (e.g., excessive redness, swelling, bruising, soreness, altered sensation, etc.) to the investigator between and at follow-up visits. Noninvasive ultrasound may be used to assess the volume and location of the soft tissue treated below the dermis. Photography and/or videography may be obtained.

The subject will be scheduled and instructed regarding their follow-up visits and discharged from the clinic.

#### 2.6.3. Visit 3/ Maintenance (Day 7) & Visit 4/Maintenance (Day 30)

Subject will be evaluated and data collected per the schedule of events. (Appendix B). Any changes in concomitant medications/concurrent procedures will be assessed. Any anticipated observations, adverse events, and/or SAE/UADE of the previous treatment site(s) will be documented and accessed. Non-invasive ultrasound imaging of the treatment area may be captured. Photography may be taken of the treatment area.

#### 2.6.4. Visit 5/Study Exit (Day 56) – Telephone Follow-Up

Subject will be contacted via telephone and data collected since the last visit per the schedule of events. Any changes in concomitant medications/concurrent procedures will be assessed. Any anticipated

## CONFIDENTIAL & PROPRIETARY Page 13 of 45

observations, adverse events, and/or SAE/UADE of the previous treatment site(s) will be documented.

If the treatment effect remains at Day 56, the subject will be followed every four (4) weeks via telephone until there is no longer any effect noted, up to a total of 112 days post-treatment. Any clinically significant adverse event will be followed until resolution. The subject will exit the study once there are no longer treatment effects and no ongoing clinically significant events.

Study exit data will be collected and the subject reminded to contact the investigator if any new, previously unreported event occurs related to the treatment.

A subject is considered to have exited the study after completing all scheduled visits. In the event that a subject does not attend a scheduled visit, every effort will be made to reschedule. In the event of a subject lost to follow-up, study exit form will be completed and efforts documented.

If a subject decides to withdraw participation early, the subject will be requested to complete a final study visit and exit the study. The investigator or sponsor may at any time during the study remove a subject if there is any potential safety issue or non-compliance. In all cases, every attempt will be made to complete a final study visit.

